4.3 Screening, assessments, and follow-up

* Must be completed to confirm eligibility prior to completing other baseline measurements.

Recruitment and Telephone Screening

Potential participants will be recruited from the general population in the North/Central Florida area through general mailings and advertisements and targeted outreach to those who have consented to participate in the Claude D. Pepper Recruitment Registry (IRB#417-2007).

Potential participants who verbally consent to complete the telephone screening are assessed of the main eligibility criteria, including:

- Age
- Self-reported sedentariness
- Self-reported mobility difficulty
- Self-reported height and weight
- Medical history
- Current dietary pattern

Screening/Baseline Clinic Visit

Those who qualify based on the telephone screening are invited to take part in the in person clinic visit. During this visit, informed consent is obtained and the following assessments are completed:

- Measurement of height and weight to determine body mass index
- 4 m walk test

If the participant is eligible to participate based on these assessments, he/she will then continue with the remainder of the baseline assessments, including:

- Measurement of waist circumference
- 6 minute walk test
- Grip strength test
- Collection of blood sample for the measurement of inflammation biomarkers (IL-6 and CRP)
- Montreal Cognitive Assessment
- Fatigability Questionnaire
- SF-12
- Distribute food intake and sleep time record diaries
- Distribute activity monitor

Weekly Phone Contacts

Participants will be contacted by phone at the end of weeks 1, 2, and 3. The following will be reviewed:

- Time of first and last food or drink consumption over the past week
- Changes in health (adverse events)

Study staff will provide participants counseling if he/she is experiencing difficulty in adhering to the study intervention.

Additional phone calls may be made as needed, if the participant requires additional support or guidance in adhering to the study intervention.

Week 4 Follow-up Clinic Visit

Following 4 weeks of the study intervention, participants will complete a follow-up clinic visit. At this visit, baseline assessments are repeated and participants will be asked to report any changes in health since initiating the study. Additionally, participants will be asked to complete a satisfaction questionnaire and an exit interview about their experience during the study.

4.4 Intervention

Intermittent Fasting

Study participants will be asked to fast for a target of 16 hours per day for a period of 4 weeks. The first week will involve of a ramp up to a full 16-hour fasting period (Days 1-3 fast for 12-14 hours per day, Days 4-6 fast for 14-16 hours per day, Days 7-28 fast for 16 hours per day). Participants will be allowed to consume calorie-free beverages, tea, black coffee, sugar-free gum, and they will be encouraged to drink plenty of water throughout the entire intervention period. Participants will be asked to record the time of first and final food/drink consumption each day.

4.5 Outcomes

Adherence and Retention

Adherence to the study intervention is measured using food intake time diary. Participants are considered compliant to the study intervention if he/she fasts between 14 – 18 hours per day during weeks 2 - 4. Retention is measured by drop-out rate.

Tolerability

At each follow-up contact (either by phone or in person), participants are asked about any changes to their health or physical function since the previous contact. The changes are documented on the adverse event log. Participants are also asked about problems or challenges in following the study intervention. Any reported difficulties will be recorded on a progress note.

6 Minute Walk Test

The 6 Minute Walk test measures the amount of distance the participant can complete on a standard walking course in six minutes without running or overexerting themselves. Contraindications for test administration and stopping rules based on American Thoracic Society will be followed [28]. The walk test is completed at baseline and Week 4.

Grip Strength

Isometric hand grip strength is a commonly used measure of upper body skeletal muscle function and has been widely used as a general indicator of functional status [29, 30] and is completed at baseline and Week 4.

Montreal Cognitive Assessment (MoCA)

The Montreal Cognitive Assessment is a 30-point assessment of mild cognitive impairment, which assesses the domains of attention and concentration, executive functions, memory, language, visuoconstructional skills, conceptual thinking, calculations, and orientation [31]. This test is completed at baseline and Week 4. Different versions of the test are given at the two time points to avoid learning effects between repeated administrations of the test.

Fatigability Questionnaire

A self-administered, 26-item questionnaire to measure perceived mental and physical fatigability [32] is completed at baseline and Week 4.

Short Form (SF) -12 Health Survey

Self-administered, 12-item questionnaire to measure health-related quality of life is completed at baseline and Week 4.

Anthropometric Measurements

Body weight will be measured following the removal of excess clothing and shoes with calibrated scales.

Waist circumference is taken at the mid-point between the participant's lowest rib and the top of his/her hip bone. Both body weight and waist circumference measurements are completed at screening/baseline and Week 4.

Activity Monitor

A wrist activity monitor accelerometer to measure daily activity level is worn for the duration of the 4-week study intervention.

Systemic Inflammatory biomarkers. Inflammatory biomarkers (CRP and IL-6) are measured by ELISA at Screening/Baseline and the Week 4 visit.

Satisfaction Survey and Exit Interview

At the conclusion of the study, participants are asked to complete a self-administered survey of their level of satisfaction and experience with his/her study participation.

Participants will also complete an exit interview with study staff to allow sharing of additional feedback regarding study participation and the design of the full scale study protocol.

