Title: Time to Eat Study – Pilot

Investigators: [name] [name] [name] [name] [name] (Study Physician)

1. Abstract:

Growing evidence shows that low-grade chronic inflammation, characterized by elevations in plasma C-reactive protein and particularly Interleukin-6 (IL-6), is an independent risk factor of disability, impaired mobility, and lower walking speed. Low-grade chronic inflammation is a modifiable risk factor. However, it is unknown whether interventions that reduce the levels of inflammatory markers *per se* improve mobility, or avert decline in mobility in older persons.

There also remains an important need for interventions that can improve unhealthy changes in body composition that occur during aging. Given the known loss of lean mass that occurs during both aging and continuous calorie restriction, alternative approaches are needed to help older adults lose unhealthy weight while retaining larger amounts of lean mass. Our recent review suggests that a specific form of intermittent fasting, time restricted feeding, results in weight and fat loss (even when caloric intake is not limited), without significant loss of lean mass. This would be an optimal outcome for overweight, older adults and should also result in a reduction in inflammation and improvement in mobility.

To date, no study has examined the effects of time restricted feeding in older adults. Preliminary data regarding feasibility need to be gathered before a full scale trial can be effectively designed and implemented. Thus, the primary aims of this pilot study are to evaluate the safety and feasibility of time restricted feeding in an older adult population. The Time to Eat Pilot Study will also assess the variance of inflammatory markers, walking speed, physical and cognitive function, grip strength, body measurements, perceived fatigability, and activity level. This allows the refinement of the design, recruitment yields, target population, adherence, retention, and tolerability of a larger scale study.

For this 4-week pilot study, we will recruit 10 overweight, older adults who are at risk for, or with, mobility impairment, as measured by slow gait speed and self-reported mobility difficulty and self-reported sedentary lifestyle to complete. All participants will receive the time restricted feeding intervention, which will consist of fasting for approximately 16 hours per day.

2. Specific Aims:

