To date, no study has examined the effects of time restricted feeding in older adults. Preliminary data regarding feasibility need to be gathered before a full scale trial can be effectively designed and implemented. Thus, the primary aims of this pilot study are to evaluate the safety and feasibility of time restricted feeding in an overweight, older adult population. The Time to Eat Pilot Study will also assess the variance of inflammatory markers, walking speed, physical and cognitive function, grip strength, body measurements, perceived fatigability, and activity level. This allows the refinement of the design, recruitment yields, target population, adherence, retention, and tolerability of a larger scale study.

4. Research Plan:

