4.6 Statistical Analysis

Sample size estimates for pilot studies are inherently difficult because by intent, a pilot study is meant to include a smaller sample than a fully powered study. The enrollment sample of 10 participants is intended to provide sufficient data to indicate feasibility of the intermittent fasting (i.e., time restricted feeding) intervention in this study population and to provide descriptive estimates of effects.

Feasibility and acceptability of the proposed intervention in overweight, older adults will be evaluated by process variables including number of participants completing the study; adherence to study intervention, and number and severity of adverse events. We will also evaluate the participants' responses on the satisfaction survey as part of the feasibility and acceptability assessment.

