4.8 Data Safety Monitoring Plan and Data Safety Monitoring Board

Data Safety Monitoring Plan

Safety of the study participants is always our major concern. The study coordinator will record and monitor all adverse events reported at in person visits, and the study interventionist will record and monitor all adverse events reported by telephone. The Study Physician will determine the seriousness of any reported adverse events and whether or not the event is related to the study intervention.

An **adverse event** is any untoward medical occurrence associated with the use of a drug in humans, whether or not considered study related.

The event is **serious** if it results in death, is life-threatening, requires inpatient hospitalization or prolongs an existing hospitalization, results in a persistent or significant disability/incapacity, or congenital anomaly/birth defect.

Safety related events are reported in a timely fashion, as required by the DSMB and the IRBs that are responsible for study oversight.

The classification of potential relationship to the intervention is as follows.

Definite - Temporal pattern + Known or expected AE response pattern + Confirmed by stopping the intervention + Reappearance of AE on re-challenge

Possible - Temporal pattern + Known or expected AE response pattern + Could have been produced by a number of other factors

Not related - AE for which sufficient information exists to indicate that the cause is

unrelated to the study intervention

Time to Eat study participants are comprised of an overweight, moderately functioning population expected to be at high risk for acute and chronic comorbid health events.

A Data and Safety Monitoring Plan is implemented to ensure the safety of all participants involved in the study and to ensure the validity and integrity of the data. The Principal Investigator with the advice of the Study Physician monitor all aspects of safety.

Data Safety Monitoring Board

This project supported by the UF Claude D. Pepper Older Americans Independence Center (OAIC) grant (NIH P30 AG028740) and will utilize the OAIC Data Safety Monitoring Board (DSMB).

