The OAIC DSMB consists of an established board which has reviews all studies conducted within the UF OAIC. This board meets bi-annually and consists of the following individuals: (1) [name]., Chair, an epidemiologist who has been involved in research for many years, (2) [name]., a biostatistician who has been involved in numerous clinical trials, and (3) [name]., a physician who has been involved in the conduct of clinical research for many years. DSMB Reports will be provided to the UF IRB-01 with annual Continuing Review submissions.

5. Possible Discomforts and Risks:

Intermittent Fasting

Only a limited number of human clinical trials have been published to date evaluating intermittent fasting dietary interventions [33, 34]. Of the adverse effects reported in these and other studies, undesirable weight loss and hunger were the two most prominent. It is likely that it will take participants several days to start adjusting to a time restricted eating pattern. During these times, participants may experience gastrointestinal discomfort, feelings of being more or less hungry than usual, and have more or less energy at certain times of the day than they usually have. While adhering to time restricted feeding, participants may feel their blood sugar levels fluctuate up and down more rapidly than they are typically used to, which may affect their energy levels and how hungry or full they feel. Also, there is a small risk that their blood sugar levels will go too high or too low. If their blood sugar levels drop too low, they may experience dizziness, sweating, sleepiness, anxiety, hunger, or weakness. Participants will be encouraged to contact the study physician and/or PI if they become concerned while adhering to this eating pattern.

Risks associated with the blood draw. The risks of drawing blood from a vein include discomfort at the site of puncture; possible bruising and swelling around the puncture site; rarely an infection; and, uncommonly, faintness from the procedure. To minimize these risks, study staff are trained to properly draw blood and use measures that help prevent complications.

Risks associated with blood pressure measurement. The risks of placing a blood pressure cuff on a participant's arms include pinching or slight bruising. To minimize these risks, study staff are trained to appropriately administer blood pressure tests.

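### Expected effects of fasting are not asked about by name before or during the intervention, and difficulties are recorded outside the adverse event log, so the adverse event count may understate them and cannot readily separate new from pre-existing symptoms.

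*Combined protocol and SAP*

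**What the plan says.** All references are to the combined protocol and SAP.

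- **Role of safety.** Sections 1 and 3 state that "the primary aims of this pilot study are to evaluate the safety and feasibility" of the intervention, and Section 2 lists tolerability under feasibility. Section 4.6 plans to summarise safety by the "number and severity of adverse events".
- **Design.** Section 1: "All participants will receive the time restricted feeding intervention". There is no control arm. Section 4.6 justifies the size in words only: "The enrollment sample of 10 participants is intended to provide sufficient data to indicate feasibility".
- **How events are elicited.** Section 4.5, Tolerability, has two questions. In the first, "participants are asked about any changes to their health or physical function since the previous contact", and answers enter the adverse event log. For the second, "Participants are also asked about problems or challenges in following the study intervention", and answers enter a progress note.
- **When.** Table 1 schedules adverse event review at Weeks 1 to 4 and not at baseline.
- **What is expected.** Section 5 gives undesirable weight loss and hunger as the most prominent effects in published studies. It adds that "participants may experience gastrointestinal discomfort, feelings of being more or less hungry than usual", changes in energy and, if blood sugar falls, a list of symptoms that includes dizziness, sweating and weakness.
- **Who is enrolled.** Section 4.8 describes a population "expected to be at high risk for acute and chronic comorbid health events".
- **What is measured before fasting.** Medical history, vital signs, weight, the fatigability questionnaire and SF-12 (Table 1, Section 4.5).

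**The concern.** The plan says which effects it expects, but it relies on participants to raise them unprompted. If hunger or dizziness is mentioned as a difficulty with fasting rather than as a change in health, Section 4.5 sends it to a progress note, while Section 4.6 counts adverse events. The same complaint can therefore be counted or not, depending on which question drew it out.

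For hunger, gastrointestinal and low-glucose symptoms there is also no recorded level from before fasting. With no control arm and a population at high risk of other health events, a logged symptom has little to be compared with.

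At stake is the safety and tolerability result, a primary aim and an input to the larger study. It could look more favourable than the participants' experience, and it would not show which symptoms were new.

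**Working it through.** **No figure to reproduce.** The documents give no event rate, precision target or power. What follows is a comparison of the text and an illustration on stated assumptions.

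**1. Expected effects against what is collected**

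| Section 5 effect | Level before fasting | Asked by name during fasting |
|---|---|---|
| Undesirable weight loss | Weight at baseline | Not asked; weighed at Week 4 |
| Changes in energy | Partly (fatigability, SF-12) | Not at the weekly calls; questionnaires at Week 4 |
| Hunger | None described | No |
| Gastrointestinal discomfort | None described | No |
| Low-glucose symptoms | None described | No |

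Medical history may note some long-standing complaints, but it is not described as a symptom rating. The two questionnaires are repeated only at Week 4. Section 5 expects participants to need several days to start adjusting, and Section 4.4 raises the fasting time over Days 1 to 6, so an early, transient effect can pass between the two measurements.

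**2. Recall window.** Section 4.5 anchors the logged question to the last contact. Section 4.3 anchors the Week 4 question to the start of the study. Under the first, a symptom that begins in Week 1 and persists is no longer a change at Week 2, so its duration is lost. Under the second, the same symptom can be reported again at Week 4 and counted twice.

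**3. Severity.** Section 4.6 promises severity. Section 4.8 defines seriousness and relatedness, and no severity scale is given.

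**4. Chance of recording no case**

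Inputs: n = 10 (Section 4.6). Assumed, not in the documents: true frequency p = 0.30; overall probability d that an affected participant's symptom is recorded at any time in the study; participants independent and all followed.

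P(0 recorded) = (1 − p·d)^10, and expected number recorded = 10·p·d, against 10 × 0.30 = 3 true cases.

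- d = 0.30: (1 − 0.09)^10 = 0.389; expected 0.9
- d = 0.50: (1 − 0.15)^10 = 0.197; expected 1.5
- d = 0.90: (1 − 0.27)^10 = 0.043; expected 2.7

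**5. Sensitivity to what d means.** If d applied to each of the four scheduled contacts, the symptom persisted and contacts were independent, overall capture would be 1 − (1 − d)^4. That is 0.760 for d = 0.30 and 0.938 for d = 0.50. P(0 recorded) would then be (1 − 0.228)^10 = 0.075 and (1 − 0.281)^10 = 0.037. Full capture gives 0.70^10 = 0.028.

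**6. Precision.** Exact 95% intervals at n = 10 are 0% to 30.8% for 0/10 and 6.7% to 65.2% for 3/10. A low count is weak reassurance even with complete capture; incomplete capture adds a downward bias that the interval does not show.

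**The case against.** The case against has real force.

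- **There are several routes for complaints.** Besides the two questions there are as-needed calls, a satisfaction survey, an exit interview and an invitation to contact the study physician or principal investigator. This stands. The plan does not say that symptoms raised by these routes enter the event log, and for the second question it names a different record.
- **Some baseline data exist.** A reader might infer that nothing about symptoms is known before fasting. The documents do not support that: fatigability, SF-12, weight and medical history are recorded. The gap is confined to hunger, gastrointestinal and low-glucose symptoms, and to early transient changes.
- **The logged question asks about change.** A reader might infer that symptoms already present would simply be logged as events. They should not be, because a stable symptom is not a change. What remains is that the comparison rests on each participant's unaided recall.
- **Detection is not absent.** A reader might infer that the plan cannot detect expected effects. On the figures above the chance of at least one recorded case is 61% to 80%, and it is higher if capture is per contact and symptoms persist. The supportable claim is possible understatement.
- **Relatedness is judged.** Section 4.8 has the study physician classify each event, so it would be wrong to say that nothing can be attributed. The judgement has limits. The definite category requires recurrence on re-challenge, for which nothing is scheduled, and the possible category fits almost any expected symptom that has other potential causes.
- **This is a descriptive pilot of 10.** That is true, and no group-level causal claim is planned. It limits how much the point matters, but a descriptive count still depends on what was asked and where the answers were filed.

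**Conclusion.** The point holds as a weakness in ascertainment. Three features rest on the text alone: expected effects are not solicited by name, three symptom groups have no pre-fasting level, and reported difficulties are filed outside the log that feeds the count. The conflict over the Week 4 recall window also rests on the text.

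The size is illustrative. With 30% true frequency, the chance of recording no case in 10 is 39% to 20% at 30% to 50% overall capture, against 4% at 90%. None of the frequency or capture values comes from the documents. If capture is per contact and symptoms persist, the first range falls to about 7.5% to 3.7%, and most of the contrast disappears. The direction, possible understatement, is firmer than the amount.

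This does not invalidate the pilot. It is a cheap improvement to the measurement of a primary aim.

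**What to change.** 1. Keep both open questions.
2. Add a short checklist of the Section 5 symptoms, each rated 0 to 3 for the past week, at the baseline visit before Day 1, at each weekly call and at Week 4. This also supplies a stated severity rating for solicited symptoms.
3. Enter any symptom reported as a difficulty in the adverse event log as well as the progress note.
4. Reconcile the Week 4 recall window between Sections 4.3 and 4.5.
5. In Section 4.6, state that the report will give, for each symptom, the number of participants with a new or worsened rating against their own baseline, with an exact 95% interval, shown separately from spontaneously reported events.

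**Cost.** A few minutes per contact (about 2 to 3, as an estimate), with no extra visits. More mild symptoms will be recorded, which is why solicited and spontaneous events must be shown apart.

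**Limit.** The change separates new from pre-existing symptoms; it does not establish causation without a control arm. A paired sign test at this size would need at least 6 participants with a new symptom and none with a resolved one to reach two-sided p < 0.05 (2 × 0.5^6 = 0.031; 5 to 0 gives 2 × 0.5^5 = 0.063). The report should therefore stay descriptive.
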